8.0 Handling of Potential Intercurrent Events for the Primary and Key Secondary Endpoints

The efficacy endpoints are exploratory, so no handling of intercurrent events for efficacy endpoints will be provided.

9.0 Efficacy Analyses

9.1 General Considerations

All analyses on efficacy variables will be performed in the mITT population, unless stated otherwise. For monthly endpoints, baseline is defined as assessments during the last 28 days of baseline period. For efficacy endpoints that are assessed at clinical visits,

baseline is defined as the last non-missing efficacy assessment before the first dose of atogepant.

9.2 Handling of Missing Data

Descriptive statistics for efficacy endpoints will be based on observed cases (OC) only. Missing data will be handled using mixed model for repeated measures (MMRM) without imputation for the efficacy analysis for continuous endpoints unless specified otherwise.

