2.0 Study Objectives and Design

2.1 Study Objectives

To evaluate the safety and tolerability of atogepant when added to BOTOX over 24 weeks in participants with CM.

To prospectively evaluate the responder rates and change from baseline in monthly migraine days when atogepant is added to BOTOX monotherapy in participants with CM.

[figure not shown]

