2.4 Sample Size Determination

The study was powered empirically to include approximately 75 participants, as 60 participants with 6 months of exposure are required by payers to support the safety of the atogepant\BOTOX combination. An estimated early termination rate of 20% will allow for 60 participants to complete the 6-month study. 75 participants provide 95% probability to detect at least 1 occurrence of an adverse event (AE) with an incidence of $\geq 4\%$. The precision (half width of 95% confidence interval) of the estimate of change from baseline in mean monthly migraine days will be approximately 1.8 assuming an SD of 7.0 with an effective sample size of 60 participants.

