3.2 Efficacy Endpoints

All efficacy endpoints are exploratory. The definitions of the efficacy measures based on the eDiary data can be found in [Appendix B](#).

- Achievement of $\geq 25\%$, $\geq 30\%$, $\geq 50\%$, $\geq 75\%$, and 100% reduction in mean monthly migraine days across Weeks 1 to 12, Weeks 13 to 24, and at each 4-week interval
- Change from baseline in monthly migraine days across Weeks 1 to 12, Weeks 13 to 24, and at each monthly period
- Change from baseline in monthly headache days across Weeks 1 to 12, Weeks 13 to 24, and at each monthly period
- Change from baseline in monthly moderate or severe headache days across Weeks 1 to 12, Weeks 13 to 24, and at each monthly period
- Change from baseline in monthly cumulative hours of headache across Weeks 1 to 12, Weeks 13 to 24, and at each monthly period

- Change from baseline in monthly acute medication use days across Weeks 1 to 12, Weeks 13 to 24, and at each monthly period
- Change from baseline in monthly headache free days across Weeks 1 to 12, Weeks 13 to 24, and at each monthly period
- Change from baseline in monthly complete migraine symptom-free days across Weeks 1 to 12, Weeks 13 to 24, and at each monthly period
- Change from baseline in monthly cardinal migraine symptom-free days across Weeks 1 to 12, Weeks 13 to 24, and at each monthly period
- Achievement of $\geq 25\%$, $\geq 30\%$, $\geq 50\%$, $\geq 75\%$, and 100% reduction in mean monthly complete migraine symptom-free days across Weeks 1 to 12, Weeks 13 to 24, and at each 4-week interval
- Achievement of $\geq 25\%$, $\geq 30\%$, $\geq 50\%$, $\geq 75\%$, and 100% reduction in mean monthly cardinal migraine symptom-free days across Weeks 1 to 12, Weeks 13 to 24, and at each 4-week interval
- Change from baseline in monthly days with an individual non-headache symptom for each of the 5 most common non-headache symptoms (including difficulty with concentration and thinking clearly collected from AIM-D items 10 and 11) and cardinal individual non-headache symptoms across Weeks 1 to 12, Weeks 13 to 24, and at each monthly period
- Change from baseline in monthly Performance of Daily Activities domain score of the AIM-D at each monthly period
- Change from baseline in monthly Physical Impairment domain score of the AIM-D at each monthly period
- Change from baseline in monthly AIM-D total score at each monthly period
- Change from baseline in monthly AIM-D Item 10 score at each monthly period

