9.3.2 Main Analysis of Efficacy Endpoints

The migraine day responder status is defined as participants with at least 25%, 30%, 50%, 75%, and 100% reduction compared to baseline in mean monthly migraine days across Weeks 1 to 12, Weeks 13 to 24, and at each monthly period. They will be summarized using descriptive statistics. Achievement of $\geq 25\%$, $\geq 30\%$, $\geq 50\%$, $\geq 75\%$, and 100% reduction in mean monthly complete migraine symptom-free days and cardinal migraine symptom-free days will be analyzed in a similar way as migraine day responder status.

For endpoints collected from eDiary, change from baseline in monthly migraine days, headache days, moderate or severe headache days, cumulative hours of headache, acute medication use days, headache free days, complete migraine symptom-free days, cardinal migraine symptom-free days, days with individual non-headache symptom for each of the 5 most common and cardinal individual non-headache symptoms, Performance of Daily Activities domain score of the AIM-D, Physical Impairment domain score of the AIM-D, AIM-D total score, AIM-D Item 10 score, and AIM-D Item 11 score at each monthly period, they will be analyzed using a mixed-effect model for repeated measures (MMRM), including visit as a categorical fixed effect, and the baseline score, baseline-by-visit interaction as covariates. An unstructured covariance matrix will be used

to model the covariance of within-participant repeated measurements. The Kenward-Roger approximation¹ will be used to estimate the denominator degrees of freedom. The analysis will be performed based on all postbaseline monthly values using only the observed cases without imputation of missing values. The treatment effect across Weeks 1 to 12, Weeks 13-24 and at each monthly will be estimated by the least square (LS) Means, along with their SE and 95% confidence intervals, and the p-value.

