For health outcome measures with a continuous response range change from baseline in the MSQ v2.1 Role Function-Preventive domain score, Role Function-Restrictive domain score and Emotional Function domain score, PHQ-9 total score, the percent work time missed, percent impairment while working, percent overall impairment, and percent activity impairment due to migraine as assessed by WPAI:MIGRAINE, GAD-7 total score, PROMIS v 2.0 Cognitive Function Abilities Subset 6a score at Weeks 4, 8, 12, 16, 20 and 24, they will be analyzed in a similar way as the above MMRM. The proportions of participants reporting "satisfied" or "extremely satisfied" and the proportions of participants with PGIC of "much better" or "very much better" at Weeks 4, 8, 12, 16, 20 and 24 will be summarized using descriptive statistics by visit.

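### Responder, PSSM and PGIC proportions are reported on observed cases only, so later rates may be inflated if participants who leave respond less often than those who stay

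*SAP*

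**What the plan says.** SAP 2.1 gives the second objective as "To prospectively evaluate the responder rates and change from baseline in monthly migraine days" when atogepant is added to BOTOX. SAP 9.3.2 defines migraine-day responders at five thresholds for Weeks 1-12, Weeks 13-24 and each month, and says of them: "They will be summarized using descriptive statistics". The PSSM and PGIC proportions at Weeks 4 to 24 "will be summarized using descriptive statistics by visit".

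The missing-data rule for such summaries is in SAP 9.2: "Descriptive statistics for efficacy endpoints will be based on observed cases (OC) only". The MMRM, which uses all observed post-baseline months, is for continuous endpoints only. SAP 8.0 adds that "no handling of intercurrent events for efficacy endpoints will be provided".

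Three other provisions decide who is observed:

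- SAP 4.0 limits efficacy analyses to the mITT population, which requires at least one evaluable post-baseline four-week period.
- SAP Appendix B treats a post-baseline month with fewer than 14 diary days as missing.
- Protocol 5.6 asks that participants who stop study drug stay in follow-up unless they withdraw consent.

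On expected attrition, SAP 2.4 says: "An estimated early termination rate of 20% will allow for 60 participants to complete the 6-month study". Neither document gives an expected responder rate, names the responder denominator, or says how a 12-week mean is formed when only one or two of its three months are evaluable.

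**The concern.** An observed-case proportion in a late period describes those still providing data. If people who leave because the add-on did not help, or was not tolerated, would have responded less often, the proportion can rise from Weeks 1-12 to Weeks 13-24 with no change in any individual. A reader could take that for growing benefit.

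The design gives no protection. In a single-arm, open-label study no control proportion is affected in the same way, so the absolute rate is itself the result. The continuous endpoints at least have a model that uses each participant's earlier months. The binary endpoints have no counterpart and no sensitivity analysis.

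**Working it through.** **Inputs.** From SAP 2.4: 75 participants, 20% early termination, 60 completers, SD 7.0. Assumed, because the documents do not give them: the observed-case rate p (50% as the worked case, 20% to 70% as the range), the rate q that leavers would have had (0% to 100%), and the number m of 75 without evaluable data in the period.

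**The plan's own figures reproduce.**

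- Completers: 75 × 0.80 = 60, so 15 terminate early.
- Probability of seeing at least one AE of 4% incidence: 1 − 0.96^75 = 0.953, against the stated 95%.
- Half-width of the 95% CI: 1.96 × 7.0/√60 = 1.77 (1.81 with t on 59 df), against the stated 1.8.

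**Size of the possible bias.** The rate over all 75 is [(75 − m)p + mq]/75, so the observed-case rate exceeds it by (m/75)(p − q). With p = 50%:

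| Missing m | Leavers' rate q | Rate over all 75 | Observed-case excess |
|---|---|---|---|
| 15 | 0% | 30/75 = 40% | 10 points |
| 15 | 25% (half of p) | 33.75/75 = 45% | 5 points |
| 15 | 50% (same as p) | 37.5/75 = 50% | 0 |
| 15 | 100% | 45/75 = 60% | −10 points |
| 10 | 0% | 32.5/75 = 43.3% | 6.7 points |
| 5 | 0% | 35/75 = 46.7% | 3.3 points |

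With m = 15 and q = 0 the excess is 0.2 × p: 4 points at p = 20% and 14 points at p = 70%.

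**How much belongs to the observed-case rule.** Some of the 15 may leave before they have any evaluable month. The mITT definition removes these, not SAP 9.2. Taking q = 0 and 30 responders among 60 observed:

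- 5 never enter the mITT: counting missing as non-response within the mITT gives 30/70 = 42.9%. Of the 10 points, 7.1 come from the observed-case rule and 2.9 from the mITT definition.
- 10 never enter: 30/65 = 46.2%. The split is 3.8 and 6.2 points.

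A sensitivity analysis confined to the mITT would therefore not recover the whole gap.

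**The case against.** **Direction.** A reader might infer that the Weeks 13-24 rates are inflated. The documents do not support that. Upward bias needs q < p, and nothing in either document gives leavers' response. Protocol 5.5 lists reasons for leaving with no necessary link to efficacy, such as pregnancy and noncompliance. With q = p there is no bias, and with q > p the observed-case rate is too low. This part of the objection stands.

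**Amount.** A reader might also take 20% as the missing fraction in Weeks 13-24. It is a planning assumption about completing six months. Participants who stop drug are to be followed, 14 diary days make a month evaluable, and someone who leaves after an evaluable Weeks 13-16 month may still count. This also stands, but it does not remove the concern. Withdrawal of consent ends follow-up, and Protocol 5.5 provides for withdrawal from the study, not just from drug, for some adverse events. Whether one evaluable month is enough cannot be settled because the SAP gives no rule.

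**Status.** SAP 3.2 states: "All efficacy endpoints are exploratory". Safety is the primary objective, no responder rate is tested, and monthly migraine days also have an MMRM estimate with a 95% CI. So no confirmatory claim is at risk. The rate is still a named objective, though, and will be read as an absolute figure.

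**Remedy.** Counting missing as failure is an assumption too. It treats a month of poor diary compliance as treatment failure, and it biases downward if absence is unrelated to response. That is a good reason not to make it the headline, but not a reason to leave it out as a bound.

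**Conclusion.** The concern holds as a risk, not as a demonstrated bias. Later responder, PSSM and PGIC proportions drop anyone without evaluable data in the period, and the plan offers nothing to show how much that matters. At an assumed observed-case rate of 50%, the overstatement in Weeks 13-24 is at most 10 points at the planned attrition. That figure requires all 15 early terminators to be missing and none to respond. It is 5 points if they respond at half the observed rate, 3.3 to 6.7 points if only 5 to 10 of 75 are missing and none responds, and zero if they respond equally. The bound scales with the assumed rate and would be larger if more than 15 were missing. What is affected is the reading of an exploratory descriptive rate. A bound should still be reported, because the rate is a stated objective and has no comparator.

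**What to change.** Keep the observed-case proportion and, for each period, add a sensitivity proportion beside it that counts a missing or non-evaluable period as non-response.

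- **Denominator.** For migraine-day responders, use all treated participants with an evaluable eDiary baseline. For PSSM and PGIC, use all treated participants: the activity schedule has no baseline assessment of either, so a diary baseline has no role there.
- **Reporting.** Give exact 95% confidence intervals and both n's, and label the added row as a conservative bound.
- **Partial windows.** State how the Weeks 1-12 and Weeks 13-24 means, and the responder status based on them, are formed when only one or two months are evaluable.
- **Population.** Say that the added row uses a wider set than the mITT, since both documents assign efficacy analyses to the mITT, and record it under SAP 15.1 as an added sensitivity analysis.

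The cost is one extra row per table, a few sentences in the SAP, and a second figure less favourable than the first. No new data are needed, and the endpoints remain exploratory.

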9.3 Efficacy Endpoints and Analyses

9.3.1 Efficacy Endpoints

The exploratory efficacy endpoints are listed in Section [3.2](#).

9.3.2 Main Analysis of Efficacy Endpoints

The migraine day responder status is defined as participants with at least 25%, 30%, 50%, 75%, and 100% reduction compared to baseline in mean monthly migraine days across Weeks 1 to 12, Weeks 13 to 24, and at each monthly period. They will be summarized using descriptive statistics. Achievement of $\geq 25\%$, $\geq 30\%$, $\geq 50\%$, $\geq 75\%$, and 100% reduction in mean monthly complete migraine symptom-free days and cardinal migraine symptom-free days will be analyzed in a similar way as migraine day responder status.

For endpoints collected from eDiary, change from baseline in monthly migraine days, headache days, moderate or severe headache days, cumulative hours of headache, acute medication use days, headache free days, complete migraine symptom-free days, cardinal migraine symptom-free days, days with individual non-headache symptom for each of the 5 most common and cardinal individual non-headache symptoms, Performance of Daily Activities domain score of the AIM-D, Physical Impairment domain score of the AIM-D, AIM-D total score, AIM-D Item 10 score, and AIM-D Item 11 score at each monthly period, they will be analyzed using a mixed-effect model for repeated measures (MMRM), including visit as a categorical fixed effect, and the baseline score, baseline-by-visit interaction as covariates. An unstructured covariance matrix will be used

to model the covariance of within-participant repeated measurements. The Kenward-Roger approximation¹ will be used to estimate the denominator degrees of freedom. The analysis will be performed based on all postbaseline monthly values using only the observed cases without imputation of missing values. The treatment effect across Weeks 1 to 12, Weeks 13-24 and at each monthly will be estimated by the least square (LS) Means, along with their SE and 95% confidence intervals, and the p-value.

For health outcome measures with a continuous response range change from baseline in the MSQ v2.1 Role Function-Preventive domain score, Role Function-Restrictive domain score and Emotional Function domain score, PHQ-9 total score, the percent work time missed, percent impairment while working, percent overall impairment, and percent activity impairment due to migraine as assessed by WPAI:MIGRAINE, GAD-7 total score, PROMIS v 2.0 Cognitive Function Abilities Subset 6a score at Weeks 4, 8, 12, 16, 20 and 24, they will be analyzed in a similar way as the above MMRM. The proportions of participants reporting "satisfied" or "extremely satisfied" and the proportions of participants with PGIC of "much better" or "very much better" at Weeks 4, 8, 12, 16, 20 and 24 will be summarized using descriptive statistics by visit.

10.0 Safety Analyses

10.1 General Considerations

Safety data will be summarized for the safety population. The safety parameters will include AEs, clinical laboratory tests (hematology, chemistry, and urinalysis), ECGs, vital signs, and the C-SSRS. For each safety parameter, the last non-missing safety assessment before the first dose of atogepant will be used as the baseline for all analyses of that safety parameter. Continuous variables will be summarized by number of participants and mean, SD, median, Q1, Q3, minimum, and maximum values. Categorical variables will be summarized by number and percentage of participants.

10.2 Adverse Events

Adverse events will be summarized and presented using primary MedDRA SOC and PTs according to the version of the MedDRA coding dictionary used for the study at the time of database lock. The actual version of the MedDRA coding dictionary used will be noted in the AE tables and in the clinical study report. Specific adverse events will be counted once for each participant for calculating percentages, unless stated otherwise. In addition, if the same adverse event occurs multiple times within a participant, the highest severity and level of relationship to investigational product will be reported.

10.2.1 Treatment-Emergent Adverse Events

Treatment-emergent AEs (TEAEs) are defined as any AE with the onset that is after the first dose of study drug. Events when the onset date is the same as the study drug start date are assumed to be treatment-emergent. An AE that occurs more than 30 days after the last dose of open-label study treatment will not be counted as a TEAE. All TEAE will be summarized overall, as well as by primary MedDRA SOC and PT. The SOC will be presented in alphabetical order, and the PTs will be presented in alphabetical order within each SOC.

The number and percentage of participants experiencing TEAEs will be summarized.

An AE will be considered a treatment-emergent serious AE (TESAE) if it is a TEAE that additionally meets any SAE criterion.

TEAEs that started after the date of last dose of study treatment will be considered as newly emergent.

10.2.2 Adverse Event Overview

An overview of AEs will be presented consisting of the number and percentage of participants experiencing at least one event for each of the following AE categories:

- Any TEAE

- Any TEAE related to study treatment according to the investigator
- Any severe TEAE
- Any TESA
- Any TEAE leading to discontinuation of study treatment
- Any TEAE leading to death
- All deaths

10.2.3 Treatment-Emergent Adverse Events by SOC and/or PT

Treatment-emergent adverse events will be summarized by SOC and PT; by maximum relationship to study treatment as assessed by the investigator (e.g., reasonable possibility or no reasonable possibility) and SOC and PT; by maximum severity and SOC and PT; and by participant number and SOC and PT. Specific adverse events will be counted once for each participant for calculating percentages, unless stated otherwise. In addition, if the same adverse event occurs multiple times within a participant, the highest severity and level of relationship to investigational product will be reported.

The number and percentage of participants reporting newly emergent TEAEs will be summarized by system organ class and preferred term.

The incidence of common ($\geq 2\%$ of participants) TEAEs will be summarized by preferred term and sorted by decreasing frequency.

10.2.4 Deaths, Serious Adverse Events, and Adverse Events Leading to Study Treatment Discontinuation

Treatment-emergent serious adverse events and TEAEs leading to premature discontinuation of study treatment will be summarized by SOC and PT.

Tabular listings will be provided for all deaths, all SAEs, TESAEs, TEAEs leading to death, and TEAEs leading to premature discontinuation of study treatment.

10.2.5 Adverse Events of Special Interest

An adverse event of special interest (serious or nonserious) is one of scientific and medical concern specific to the sponsor's study intervention or program, which warrants ongoing monitoring and rapid communication by the investigator to the sponsor. Such an event might warrant further investigation in order to characterize and understand it.

Adverse Events of Special Interest (AESI) are defined in [Appendix C](#).

The summaries of above are described in the corresponding SAP Section [10.3](#).

10.3 Analysis of Laboratory Data

Data collected from central laboratories, including additional laboratory testing due to an SAE, will be used in all analyses, except for Baseline where SAE-related laboratory assessments on or before the first dose of study drug will be excluded. The clinical laboratory tests defined in the protocol operations manual (e.g., hematology, clinical chemistry, and urinalysis) will be summarized.

Each laboratory variable will be summarized for all time points (starting with Baseline) with the number of non-missing observations, mean and standard deviation, median, Q1, Q3, minimum and maximum. Mean change from baseline to each applicable post-baseline visit will be summarized, with the number of observations, baseline mean, and visit mean. The change from baseline mean will be presented for the mean change from baseline. In addition, descriptive statistics for values and changes from the baseline values in conventional units at each assessment time point will be presented for selected clinical laboratory parameters listed in [Appendix E](#). A description of reporting the lab values in conventional units in patient narratives (along with the standard reporting in SI units) is presented at the end of [Appendix E](#).

Changes in laboratory parameters will be tabulated using shift tables categorized as low, normal, or high based on the normal ranges of the laboratory used for each sample. A shift table will be provided to summarize shifts from baseline to the final post-baseline value.

Laboratory abnormalities will be evaluated based on Potentially Clinically Significant (PCS) criteria (Appendix Table D-1). For each laboratory PCS criterion, the number and percentage of participants who have a laboratory value meeting the criteria will be summarized. Listings will be provided to summarize participant-level laboratory data for participants meeting PCS criteria.

In addition, ALT, AST, alkaline phosphatase, and total bilirubin will be categorized in Table D-2. The number and percentage of participants meeting each of the criteria for postbaseline hepatic laboratory abnormalities listed in Table D-2 will be summarized. The percentages will be calculated relative to the number of participants with at least 1 available postbaseline assessment. The numerator will be the total number of participants having at least 1 postbaseline value that meets the specific category during the study. A supportive listing will also be provided.

The number and percentage of participants with an adjudicated case (i.e., $ALT \geq 3 \times ULN$ and/or $AST \geq 3 \times ULN$) will be summarized by relationship of ALT or AST elevation to study medication. The percentages will be calculated relative to the number of participants with at least 1 adjudicated case. The numerator will be the number of participants with at least 1 adjudicated case in the specific category of relationship. If a participant has more than 1 adjudicated case, he or she will be counted in the most relevant category of relationship.

Participants with an adjudicated case (i.e., $ALT \geq 3 \times ULN$ or $AST \geq 3 \times ULN$) will be listed with their ALT and AST assessments, adjudication dates, relationship of ALT or AST elevation to study medication, and confounding factor(s). Additional listings will be provided for participants who meet $ALT \geq 3 \times ULN$ or $AST \geq 3 \times ULN$ and/or potential Hy's law and have one of the following categories: at least 1 abnormal liver biochemistry risk factor, at least 1 liver disease sign and symptom, at least 1 liver diagnostic test performed, consultation with a specialist for liver evaluation, liver lab tests performed, and drug screen performed, respectively.

A listing of possible Hy's Law cases, defined as those who meet all of the following conditions simultaneously, will be provided: $ALT \geq 3 \times ULN$ or $AST \geq 3 \times ULN$ that is associated with an increase in bilirubin $\geq 2 \times ULN$ and alkaline phosphatase $< 2 \times ULN$.

A listing of urine pregnancy test results will be provided for female participants of childbearing potential with at least one positive result.

